6.6.2 Other Allowed Dose Interruptions for Pembrolizumab

Pembrolizumab may be interrupted for situations other than treatment-related AEs, such as medical/surgical events or logistic reasons not related to study therapy. Participants should be returned to study therapy within 3 weeks of the scheduled interruption, unless otherwise discussed with the Sponsor. The reason for interruption should be documented in the participant's study record. Imaging should not be delayed for delays in treatment cycles.

6.7 Intervention After the End of the Study

There is no study-specified intervention following the end of the study.

6.8 Clinical Supplies Disclosure

NOTE: As of Amendment 011-03, this section is no longer applicable.

The emergency unblinding call center will use the intervention/randomization schedule for the study to unblind participants and to unmask study intervention identity. The emergency unblinding call center should only be used in cases of emergency (see Section 8.1.10). In the event that the emergency unblinding call center is not available for a given site in this study, the central electronic intervention allocation/randomization system (IRT) should be used to unblind participants and to unmask study intervention identity. The Sponsor will not provide random code/disclosure envelopes or lists with the clinical supplies.

6.9 Standard Policies

NOTE: As of Amendment 011-03, all participants will receive open-label pembrolizumab monotherapy.

At the close of the study after unblinding, a letter is to be sent by the investigator to those participants who received placebo in the image of the competitor's product to provide the following advice:

“You have participated in a study conducted by the Sponsor. This letter is to advise you that you were among those who received a look-alike capsule provided by the Sponsor to resemble the drug lenvatinib as much as possible. You did not receive the active drug lenvatinib as provided by MSD.”

7 DISCONTINUATION OF STUDY INTERVENTION AND PARTICIPANT WITHDRAWAL

7.1 Discontinuation of Study Intervention

Discontinuation of study intervention does not represent withdrawal from the study.

As certain data on clinical events beyond study intervention discontinuation may be important to the study, they must be collected through the participant's last scheduled follow-up, even if the participant has discontinued study intervention. Therefore, all participants

who discontinue study intervention prior to completion of the protocol-specified treatment period will still continue to participate in the study as specified in Section 1.3 and Section 8.10.4.

Participants may discontinue study intervention at any time for any reason or be discontinued from the study intervention at the discretion of the investigator should any untoward effect occur. In addition, a participant may be discontinued from study intervention by the investigator or the Sponsor if study intervention is inappropriate, the study plan is violated, or for administrative and/or other safety reasons. Specific details regarding procedures to be performed at study intervention discontinuation are provided in Section 8.1.9.

A participant must be discontinued from study intervention but continue to be monitored in the study for any of the following reasons:

- The participant or participant's legally acceptable representative requests to discontinue study intervention.
- ALT or AST elevation meeting the following criteria:
 - ALT or AST $> 5 \times$ ULN for more than 2 weeks
 - ALT or AST $> 3 \times$ ULN and (TBL $> 2 \times$ ULN or INR > 1.5)
 - ALT or AST $> 3 \times$ ULN with appearance of fatigue, nausea, vomiting, RUQ pain/tenderness, fever, rash, and/or eosinophilia ($>5\%$)
- The participant interrupts study drug administration for >12 weeks for pembrolizumab, except if agreed to by the Sponsor.
- The participant has a medical condition or personal circumstance which, in the opinion of the investigator and/or Sponsor, places the participant at unnecessary risk from continued administration of study intervention.
- The participant has a confirmed positive serum pregnancy test.
- Disease progression is radiographically documented per RECIST 1.1.

Note: If a participant has unconfirmed PD and is clinically stable*, the assigned study intervention per protocol may be continued at the investigator's discretion until PD is confirmed at least 28 days from the date of imaging suggesting PD. If subsequent imaging does not confirm PD, the participant should continue to receive study intervention and imaging to monitor disease status should continue as per SOC.

*Clinical stability is defined as:

- Absence of symptoms and signs (including worsening of laboratory values) indicating clinically significant disease progression
- No decline in ECOG performance status
- Absence of disease progression or progressive tumor at critical anatomic sites (eg, cord compression) requiring urgent alternative medical intervention
- The participant has intercurrent illness preventing further administration of study intervention.
- The participant has any progression or recurrence of any malignancy, or any occurrence of another malignancy that requires active treatment. Exceptions to secondary malignancy include basal cell carcinoma of the skin, squamous cell carcinoma of the skin, new nonulcerated primary melanoma <1 mm in depth with no nodal involvement, or carcinoma in situ (eg, breast carcinoma, cervical cancer in situ) that have undergone potentially curative therapy. Exceptions should be discussed with the Sponsor before continuing therapy or follow-up.
- The participant has unacceptable toxicities (Section 6.6).
- The investigator decides to discontinue study intervention.
- The participant has recurrent Grade 2 pneumonitis.

The participants must be discontinued from pembrolizumab treatment after completing 35 cycles of Initial Treatment (approximately 2 years) with pembrolizumab, and, if applicable, after 17 cycles (approximately 1 year) of Second Course treatment with pembrolizumab (Section 4.3.3).

Discontinuation of pembrolizumab may be considered for participants who have attained a confirmed CR and have been treated for at least 8 cycles (at least 24 weeks), receiving at least 2 doses of pembrolizumab beyond the date when the initial CR was declared.

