6.6.1.1 Immune-related Events and Dose Modification (Withhold, Treat, Discontinue)

Dose Modification and Toxicity Management for Immune-related Adverse Events Associated with Pembrolizumab

AEs associated with pembrolizumab exposure may represent an immune-related response. These irAEs may occur shortly after the first dose or several months after the last dose of pembrolizumab treatment and may affect more than one body system simultaneously. Therefore, early recognition and initiation of treatment is critical to reduce complications. Based on existing clinical study data, most irAEs were reversible and could be managed with interruptions of pembrolizumab, administration of corticosteroids and/or other supportive care. For suspected irAEs, ensure adequate evaluation to confirm etiology or exclude other causes. Additional procedures or tests such as bronchoscopy, endoscopy, skin biopsy may be included as part of the evaluation.

Dose Modification and Toxicity Management Guidelines for irAEs associated with pembrolizumab monotherapy, coformulations, or IO combinations are provided in [Table 3](#).

Of note, any serious changes to the skin, including Stevens-Johnson syndrome or toxic epidermal necrolysis, require immediate discontinuation of pembrolizumab.

Table 3 Dose Modification and Toxicity Management Guidelines for Immune-related Adverse Events Associated With Pembrolizumab Monotherapy, Coformulations or IO Combinations

General instructions:				
irAEs	Toxicity Grade (CTCAEv4.0)	Action With Pembrolizumab Monotherapy, Coformulations or IO Combinations	Corticosteroid and/or Other Therapies	Monitoring and Follow-up
Pneumonitis	Grade 2	Withhold	
 Administer corticosteroids (initial dose of 1-2 mg/kg prednisone or equivalent) followed by taper 	
 Monitor participants for signs and symptoms of pneumonitis Evaluate participants with suspected pneumonitis with radiographic imaging and initiate corticosteroid treatment Add prophylactic antibiotics for opportunistic infections
	Recurrent Grade 2 or Grade 3 or 4	Permanently discontinue		

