Diarrhea / Colitis	Grade 2 or 3	Withhold	
 Administer corticosteroids (initial dose of 1-2 mg/kg prednisone or equivalent) followed by taper 	
 Monitor participants for signs and symptoms of enterocolitis (ie, diarrhea, abdominal pain, blood or mucus in stool with or without fever) and of bowel perforation (ie, peritoneal signs and ileus) Participants with \geqGrade 2 diarrhea suspecting colitis should consider GI consultation and performing endoscopy to rule out colitis Participants with diarrhea/colitis should be advised to drink liberal quantities of clear fluids. If sufficient oral fluid intake is not feasible, fluid and electrolytes should be substituted via IV infusion.
	Recurrent Grade 3 or Grade 4	Permanently discontinue		

irAEs	Toxicity Grade (CTCAEv4.0)	Action With Pembrolizumab Monotherapy, Coformulations or IO Combinations	Corticosteroid and/or Other Therapies	Monitoring and Follow-up
AST / ALT Elevation or Increased Bilirubin	Grade 2	Withhold	
 Administer corticosteroids (initial dose of 0.5-1 mg/kg prednisone or equivalent) followed by taper 	
 Monitor with liver function tests (consider weekly or more frequently until liver enzyme value returned to baseline or is stable)
	Grade 3 or 4	Permanently discontinue	
 Administer corticosteroids (initial dose of 1-2 mg/kg prednisone or equivalent) followed by taper 	
T1DM or Hyperglycemia	New onset T1DM or Grade 3 or 4 hyperglycemia associated with evidence of β -cell failure	Withhold ^a	
 Initiate insulin replacement therapy for participants with T1DM Administer anti-hyperglycemic in participants with hyperglycemia 	
 Monitor participants for hyperglycemia or other signs and symptoms of diabetes
Hypophysitis	Grade 2	Withhold	
 Administer corticosteroids and initiate hormonal replacements as clinically indicated 	
 Monitor for signs and symptoms of hypophysitis (including hypopituitarism and adrenal insufficiency)
	Grade 3 or 4	Withhold or permanently discontinue ^a		
Hyperthyroidism	Grade 2	Continue	
 Treat with non-selective beta-blockers (eg, propranolol) or thionamides as appropriate 	
 Monitor for signs and symptoms of thyroid disorders

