	Grade 3 or 4	Withhold or Permanently discontinue ^a		

irAEs	Toxicity Grade (CTCAEv4.0)	Action With Pembrolizumab Monotherapy, Coformulations or IO Combinations	Corticosteroid and/or Other Therapies	Monitoring and Follow-up
Hypothyroidism	Grade 2-4	Continue	
 Initiate thyroid replacement hormones (eg, levothyroxine or liothyronine) per standard of care 	
 Monitor for signs and symptoms of thyroid disorders
Nephritis and renal dysfunction	Grade 2	Withhold	
 Administer corticosteroids (prednisone 1-2 mg/kg or equivalent) followed by taper 	
 Monitor changes of renal function
	Grade 3 or 4	Permanently discontinue		
Myocarditis	Grade 1	Withhold	
 Based on severity of AE administer corticosteroids 	
 Ensure adequate evaluation to confirm etiology and/or exclude other causes
	Grade 2, 3, or 4	Permanently discontinue		
All Other irAEs	Persistent Grade 2	Withhold	
 Based on severity of AE administer corticosteroids 	
 Ensure adequate evaluation to confirm etiology or exclude other causes
	Grade 3	Withhold or discontinue ^b		
	Recurrent Grade 3 or Grade 4	Permanently discontinue		

AE(s)=adverse event(s); ALT=alanine aminotransferase; AST=aspartate aminotransferase; CTCAE=Common Terminology Criteria for Adverse Events; DRESS=Drug Rash with Eosinophilia and Systemic Symptom; GI=gastrointestinal; IO=immuno-oncology; ir=immune related; IV=intravenous; SJS=Stevens-Johnson Syndrome; T1DM=type 1 diabetes mellitus; TEN=Toxic Epidermal Necrolysis; ULN=upper limit of normal.

Note: Non-irAE will be managed as appropriate, following clinical practice recommendations.

^a The decision to withhold or permanently discontinue pembrolizumab monotherapy, coformulations or IO combinations is at the discretion of the investigator or treating physician. If control achieved or \leq Grade 2, pembrolizumab monotherapy, coformulations or IO combinations may be resumed.

^b Events that require discontinuation include, but are not limited to: Guillain-Barre Syndrome, encephalitis, myelitis, DRESS, SJS, TEN and other clinically important irAEs (eg, vasculitis and sclerosing cholangitis).

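### For a suspected immune-related Grade 2 ALT/AST rise above 3×ULN with symptoms, high INR or raised bilirubin, Table 3 says withhold and Section 7.1 says discontinue, with no visible rule on which governs

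*Protocol*

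**What the plan says.** **Section 7.1 (Discontinuation of Study Intervention).** The list is mandatory, and any one reason is enough: "A participant must be discontinued from study intervention but continue to be monitored in the study for any of the following reasons". It has three hepatic criteria, none limited by cause:

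- ALT or AST above 5×, "ULN for more than 2 weeks";
- ALT or AST above 3×ULN together with total bilirubin above 2×, "ULN or INR > 1.5";
- ALT or AST above 3×ULN "with appearance of fatigue, nausea, vomiting, RUQ pain/tenderness, fever, rash, and/or eosinophilia" (eosinophilia above 5%).

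Further down, the same list gives unacceptable toxicities as a reason and points to Section 6.6.

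**Section 6.6.1.1, Table 3.** The row "AST / ALT Elevation or Increased Bilirubin" is driven by the column "Toxicity Grade (CTCAEv4.0"). Grade 2 is Withhold with a corticosteroid taper; Grade 3 or 4 is Permanently discontinue. The monitoring entry is "Monitor with liver function tests (consider weekly or more frequently until liver enzyme value returned to baseline or is stable"). The row has no condition on symptoms, on INR, or on transaminases and bilirubin in combination, and it does not point to Section 7.1.

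**Scope of Table 3.** It covers immune-related events: "Note: Non-irAE will be managed as appropriate, following clinical practice recommendations". Section 6.5.4 adds that the guidance need not be followed once an event is judged unrelated to pembrolizumab.

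**The concern.** A hold and a discontinuation are different actions in this protocol. Section 6.6.1 allows pembrolizumab to be interrupted for up to 12 weeks, and Section 7.1 treats a longer interruption as a separate reason to discontinue. As of Amendment 011-04, a participant who discontinues pembrolizumab leaves the study after the Safety Follow-up visit, and Second Course is no longer offered (Sections 1.3.1 and 4.1). The document history says that the study was kept open so that remaining participants would have continued access to pembrolizumab. For a liver event to which both passages apply, following one rather than the other can decide whether the participant stays on study drug.

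**Working it through.** The plan gives no figure to reproduce, so this is a comparison of text with one unknown.

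**Inputs.** The thresholds of 3×ULN, 5×ULN for more than 2 weeks, TBL 2×ULN and INR 1.5 come from Section 7.1. The actions by grade come from Table 3. The upper limit of Grade 2 for ALT/AST, called *u* (in ×ULN), is not printed in the documents. It is treated as an assumption and varied. Grade 2 is taken to begin at or below 3×ULN; if it began higher, the band below would start there instead.

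**Step 1: where Grade 2 overlaps Section 7.1.** The second and third hepatic criteria need ALT or AST above 3×ULN, and Grade 2 ends at *u*. The overlap is therefore above 3 up to *u*, with width *u* − 3:

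| Assumed *u* (×ULN) | Overlap | Width |
|---|---|---|
| 3 or lower | none | 0 |
| 4 | >3 to 4 | 4 − 3 = 1 |
| 5 | >3 to 5 | 5 − 3 = 2 |

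For *u* of 5 or lower, no Grade 2 value can meet the first criterion (above 5×ULN for more than 2 weeks).

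**Step 2: the two rules side by side, for a suspected immune-related rise.**

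| Finding | Table 3 | Section 7.1 hepatic criteria | Conflict? |
|---|---|---|---|
| Grade 2, in the overlap, with a listed symptom or eosinophilia | Withhold | Discontinue | Yes |
| Grade 2, in the overlap, INR >1.5 | Withhold | Discontinue | Yes |
| Grade 2, in the overlap, TBL >2×ULN, bilirubin Grade 2 or lower | Withhold | Discontinue | Yes |
| Same, but bilirubin Grade 3 or 4 | Permanently discontinue (bilirubin is in the row) | Discontinue | No |
| Grade 2, none of these findings | Withhold | Not triggered | No |
| Grade 3 or 4, any Section 7.1 criterion met | Permanently discontinue | Discontinue | No |
| Grade 3 or 4, short-lived, no other finding | Permanently discontinue | Not yet triggered | Not firm (step 3) |

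**Step 3: Grade 3 or 4 without a hepatic criterion.** The Section 7.1 reasons add together, so an unmet reason is not an instruction to continue. The unacceptable-toxicities reason, which cites Section 6.6, can carry Table 3's Grade 3 or 4 action into Section 7.1.

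**Step 4: does that link also settle the Grade 2 rows?** No. It is a general pointer that sets no precedence. It neither turns a Grade 2 hold into a discontinuation nor releases a participant from a hepatic criterion already met. By contrast, recurrent Grade 2 pneumonitis is a permanent discontinuation in Table 3 and a listed reason in Section 7.1, so the two places do agree for that event.

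**The case against.** The best defence is that the two passages work as layers. Table 3 gives a grade-based first action for events attributed to pembrolizumab. Section 7.1, worded as a requirement and blind to cause, adds a stop when further findings appear. A site applying both would discontinue, and there would be no practical conflict. This is a plausible reading, but no visible text states it, and the Table 3 row does not tell a site to look for those further findings.

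Three other points limit the concern. The overlap depends on a grading cut-off that the documents do not print. The heading for general instructions in Table 3 has no text under it in the copy available to us, so a precedence statement or cut-offs may be there. Section 8.4.7 sends sites to the Investigator Study File Binder for the combined transaminase and bilirubin pattern, and that binder is not among the documents. All three stand as qualifications. None removes the conflict in the text that can be read.

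A reader might also infer more than the documents support:

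- *The rules disagree whatever the Grade 2 cut-off.* At a limit of 3×ULN or lower the hold/discontinue overlap disappears. What remains is the Grade 3 difference, which the Section 6.6 reason largely answers.
- *The interruption and discontinuation counts in Table 9 will vary by site.* Table 9 does summarise the two separately, but nothing in the documents shows how sites resolve the conflict or how many participants are affected.

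**Conclusion.** The concern holds in a narrow, conditional form. It covers suspected immune-related ALT/AST rises of Grade 2 that exceed 3×ULN and come with a listed symptom or eosinophilia, with INR above 1.5, or with total bilirubin above 2×ULN while bilirubin is itself Grade 2 or lower. It rests on the assumption that Grade 2 extends above 3×ULN, and on there being no precedence statement in the Table 3 instructions that we could not see. Isolated Grade 2 rises, events judged unrelated to pembrolizumab, and Grade 3 or 4 rises are outside it. The number of participants affected cannot be derived. The point merits correction because it bears on whether participants keep study drug. It does not bear on the efficacy analyses, and no view is taken on which clinical rule is right.

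**What to change.** First check the general instructions of Table 3 for a statement of precedence. If there is none, reconcile Section 7.1 with the hepatic row of Table 3 so that one set of findings leads to one action. Alternatively, state in both places which passage governs for suspected immune-related liver events and which for other causes. Printing or citing the ALT/AST and bilirubin limits for each grade beside the row would also let a reader see whether the two rules overlap. Which action applies is the sponsor's clinical decision. The cost is a sentence or cross-reference in each place, with no added tests or visits.

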Intervention Group Name	Drug	Dose Strength	Dose Frequency	Route of Admin	Treatment Period	Use															
Arm 1 and 2	Pembrolizumab	200 mg	Q3W	IV Infusion	~2 years (initial treatment) ~1 year (Second Course)	Background Treatment															
Total Number	Note: As of Amendment 011-03, all participants will receive open-label pembrolizumab only. 2 arms																				
Duration of Participation	NOTE: As of Amendment 011-03, lenvatinib and placebo are removed from study intervention. All participants remaining in the study will receive open-label pembrolizumab only. Each participant will participate in the study from the time the participant signs the informed consent form (ICF) through the final protocol-specified contact. After a screening phase of up to 28 days, each participant will be assigned to receive pembrolizumab for up to 35 cycles or until a discontinuation criterion (Section 7.1) is met. Participants will be permitted to continue study intervention beyond RECIST 1.1-defined PD as long as the treating investigator considers that the participant may experience clinical benefit, and the participant is																				

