	
tolerating study intervention. All decisions to continue study intervention beyond confirmed PD by RECIST must be approved by the Sponsor.
 
Participants who have been receiving study intervention for ≥ 24 weeks (8 cycles) and who attain a CR may consider stopping pembrolizumab treatment. If a confirmed CR per RECIST 1.1 is attained, participants must receive pembrolizumab for at least 2 additional cycles after CR is first documented.
 
Participants with investigator-determined PD by RECIST 1.1 after first course treatment with pembrolizumab treatment has been completed (i.e., 35 cycles) or stopped for confirmed CR may be eligible for up to 17 additional cycles of pembrolizumab (approximately 1 year) in the Second Course Treatment phase upon experiencing PD (Section 8.10.3).
 
Note: As of Amendment 011-04, Second Course will no longer be offered. Any participant receiving Second Course treatment prior to initiation of Amendment 011-04 will be able to complete treatment as planned.
 
After the end of study intervention, each participant will be followed for safety and spontaneously reported pregnancy as described in Section 8.
 
Tumor imaging should be performed by site investigator/radiology assessment as per standard of care (SOC) for the disease and local guidelines. Imaging timing should follow calendar days and should not be adjusted for delays in cycle starts.
 
Note: As of Amendment 011-04, study participation will end after the final administration of pembrolizumab. Participants who either complete 35 administrations of pembrolizumab or discontinue pembrolizumab will discontinue from the study following the Safety Follow-up visit. AEs and spontaneously reported pregnancies will be reported and followed as described under Section 8.4. All participants in Efficacy Follow-up prior to initiation of Amendment 011-04 will stop efficacy assessments and be discontinued from the study. All participants in Survival Follow-up prior to initiation of Amendment 011-04 are considered to have completed the study and should have a final survival contact. The overall study ends when the last participant completes the last study-related contact or visit, withdraws from the study, or is lost to follow-up (ie, the participant is unable to be contacted by the investigator).

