Note: As of Amendment 011-04, participants who either completed pembrolizumab administration or discontinue pembrolizumab will discontinue from the study following the Safety Follow-up visit (Section 8.10.5). AEs and spontaneously reported pregnancies will be reported and followed as described under Section 8.4. All participants in Efficacy Follow-up prior to initiation of Amendment 011-04 will stop efficacy assessments and be discontinued from the study. All participants in Survival Follow-up prior to initiation of Amendment 011-04 are considered to have completed the study and should have a final survival contact; these participants will no longer be contacted for survival information.

During initial treatment, participants who have been receiving study intervention for ≥ 24 weeks (8 cycles) and who attain a CR may consider stopping pembrolizumab treatment.

If a confirmed CR per RECIST 1.1 is attained after at least 24 weeks, participants must receive pembrolizumab for at least 2 additional cycles after CR is first documented.

Adverse event monitoring will be ongoing throughout the study. AEs will be graded in severity according to the guidelines outlined in the National Cancer Institute Common Terminology Criteria for Adverse Events (NCI CTCAE) Version 4.0.

Treatment with pembrolizumab will continue for up to 35 cycles, or until a discontinuation criterion (Section 7.1) is met.

Participants who stop pembrolizumab treatment after receiving 35 administrations of pembrolizumab, or participants who have been receiving study intervention for at least 24 weeks, attain a confirmed CR, and stop study intervention may be eligible for up to 17 additional cycles (approximately 1 year) of pembrolizumab upon experiencing PD. This retreatment is termed the Second Course Treatment phase and is only available if the study remains open, the participant meets the criteria in Section 8.10.3 and upon consultation with the Sponsor. **Note: As of Amendment 011-04, Second Course will no longer be offered.** Any participant receiving Second Course treatment prior to the initiation of Amendment 011-04 will be able to complete treatment as planned.

Pembrolizumab will be administered for a maximum of 35 cycles during initial treatment and 17 cycles during the Second Course phase.

The study will be conducted in conformance with Good Clinical Practice (GCP).

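### Section 7.1 stops pembrolizumab at RECIST 1.1 progression unless PD is unconfirmed and the participant is clinically stable; the Synopsis permits continuation with no stability condition

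*Protocol*

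**What the plan says.** Protocol Section 7.1 opens its list of stopping reasons with mandatory language: "A participant must be discontinued from study intervention but continue to be monitored in the study for any of the following reasons". One listed reason is "Disease progression is radiographically documented per RECIST 1.1". The Note under it lets the investigator keep a participant on treatment when progression is unconfirmed and the participant is clinically stable, "until PD is confirmed at least 28 days from the date of imaging suggesting PD". Stability has three parts: no symptoms or signs of clinically significant progression, no ECOG decline, and no progression at a critical site that needs urgent alternative intervention.

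A later bullet in 7.1, on progression or recurrence of any malignancy and on second cancers, ends with "Exceptions should be discussed with the Sponsor before continuing therapy or follow-up".

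The Synopsis (Section 1.1, Duration of Participation) says participants are "permitted to continue study intervention beyond RECIST 1.1-defined PD as long as the treating investigator considers that the participant may experience clinical benefit", provided they tolerate it. It adds: "All decisions to continue study intervention beyond confirmed PD by RECIST must be approved by the Sponsor". The same entry says participants will "receive pembrolizumab for up to 35 cycles or until a discontinuation criterion (Section 7.1) is met". Section 4.1 repeats the deference: "Treatment with pembrolizumab will continue for up to 35 cycles, or until a discontinuation criterion (Section 7.1) is met". Section 8.10.3 also refers to 7.1 for the Second Course.

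Section 8.2.1 has treatment and imaging run until investigator-assessed RECIST 1.1 progression and mentions no exception.

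**The concern.** Both the 7.1 rule and the Synopsis permission are current text, and they set different conditions for staying on drug after progression. Expected benefit and tolerability are not the same as clinical stability. A participant can tolerate pembrolizumab, and be thought likely to benefit, while performance status is falling or disease is advancing at a critical site.

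Those are the participants whom 7.1 takes off drug. Section 6.5.2 prohibits other anticancer therapy during treatment, so continued dosing can delay a switch. Pembrolizumab is the only study drug left since Amendment 011-03, so this is the main stopping rule for everyone still treated. A site that follows the Synopsis could also commit a protocol deviation under 7.1 without knowing it.

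**Working it through.** No arithmetic applies: the plan states no figure on this point, and none can be derived. The check sets the current texts side by side. In each row, assume the participant tolerates pembrolizumab and the investigator sees possible benefit.

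| Situation | Section 7.1 | Synopsis, read alone | Section 8.2.1 |
|---|---|---|---|
| PD unconfirmed, clinically stable | May continue until PD is confirmed | May continue | Treatment runs until PD; no exception stated |
| PD unconfirmed, not clinically stable | Must stop | May continue | As above |
| PD confirmed | Stop; no clear approval route | May continue with Sponsor approval | As above |

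1. *Unconfirmed, stable.* 7.1 and the Synopsis agree. Section 8.2.1 is out of step with both because it does not refer to the 7.1 Note.

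2. *Unconfirmed, not stable.* The Note does not apply, so the mandatory stop does. The Synopsis conditions are met. The two instructions are opposite.

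3. *Confirmed.* The Note has ended. The only candidate route in 7.1 is the sentence on discussing exceptions with the Sponsor. Its bullet opens with progression of any malignancy, which could include the study cancer. The sentence itself comes directly after the list of permitted second cancers (certain skin cancers, thin melanoma, carcinoma in situ). Either reading is open, so the answer under 7.1 is unclear.

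4. *Is there another route?* Section 8.2.1.6 and Appendix 8 once gave an explicit exception after confirmed progression, following Sponsor consultation. Both are marked as no longer applicable since Amendment 011-03. The Synopsis permission remained after that body-text route was withdrawn.

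5. *Does the confirming scan have to happen?* Sections 8.2.1, 8.2.1.2 and 8.2.1.4 end imaging at progression without referring to the Note. The Note presupposes a later scan and expects standard-of-care imaging to go on if progression is not confirmed. The scan is therefore allowed but not required.

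6. *Does any analysis depend on the stopping date?* Section 9.6.1.1 dates progression at the first BICR-documented assessment whether or not study drug was stopped. Section 3 says formal comparisons between arms have ended, and Section 9 says there will be no further efficacy analyses.

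**The case against.** The strongest reply is that the Synopsis is a summary and says so: treatment lasts until a 7.1 criterion is met. On that reading its benefit and tolerability conditions add to the stability condition and do not replace it. Section 7.1 also has other stops that may catch an unstable participant, such as unnecessary risk or the investigator's decision. Section 8.1.1.1 asks for consent again at initial radiographic progression.

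Much of this stands. The deference shows which rule should govern. It does not remove a permission that follows in the same entry without the stability condition. The other stops rest on judgment, whereas the progression rule is categorical, and the consent step does not settle who must come off drug.

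Three stronger readings are tempting, and the documents do not support them:

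- *That 7.1 and the Synopsis flatly contradict each other on confirmed progression.* If the Sponsor sentence in 7.1 covers the study cancer, they agree. The Synopsis sentence is also worded as a restriction on such decisions.
- *That the gap can be sized by counting infusions up to day 28.* In 7.1 the 28 days is a minimum, and the Synopsis has no such clock, so a count would measure neither text.
- *That the imaging sections block the confirming scan.* Nothing forbids it. Leaving it to local standard of care fits a study that no longer collects these imaging data.

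**Conclusion.** The stopping rule needs correcting. There is one clear conflict, first progression in a clinically unstable participant, and one unclear route, Sponsor-approved treatment after confirmed progression. The conflict arises when the Synopsis permission is read on its own, which its wording allows despite the reference to 7.1. The imaging point is minor.

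The effect is on treatment conduct and participant safety. It is confined to participants who progress while still receiving pembrolizumab, and the documents do not say how many there are or will be. A reader might infer that PFS or the study's operating characteristics are affected. They are not: progression is dated independently of drug discontinuation, and hypothesis testing has been dropped.

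**What to change.** At the next amendment, make Section 7.1 the governing rule and align Sections 1.1 and 8.2.1 to it. Suggested text:

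> Participants with unconfirmed RECIST 1.1 PD may continue pembrolizumab only if clinically stable as defined in Section 7.1, tolerating treatment, and judged by the investigator to be potentially benefiting, until PD is confirmed on imaging at least 28 days later. After confirmed PD, pembrolizumab stops unless those same conditions hold and the Sponsor approves continuation.

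This keeps the benefit and tolerability conditions of the Synopsis and adds the missing stability condition. Whether to allow any dosing after confirmed progression is for the Sponsor to decide; if the answer is no, the last sentence should end at the stop, and the matching Synopsis sentence should be deleted.

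Optionally, add a cross-reference to the 7.1 Note in the imaging stops of Sections 8.2.1, 8.2.1.2 and 8.2.1.4, so that local standard-of-care imaging covers the confirming scan.

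The cost is a few sentences and no new data collection. Because a mandatory stopping rule is involved, an amendment suits it better than an informal memo: the Code of Conduct in Section 10.1.1 requires ethics committee approval of significant changes before they take effect, apart from urgent safety changes.
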